11. SAFETY ANALYSES

Unless otherwise specified, all safety analyses will be performed on the Full Analysis Set. The summaries will not be separated by mutational subtypes. CMMI, MDS/MPN, and Total will be reported.

11.1 Adverse events

Adverse events (AEs), including laboratory-related adverse events, will be coded by System Organ Class (SOC) and Preferred Term (PT) using MedDRA dictionary 19.0. The Investigator will grade each adverse event with NCI-CTCAE v4.03, and category the relatedness of AE to tipifarnib as either "Related" or "Not related". Treatment-emergent AEs (TEAEs) are defined as AEs with an onset on or after start of tipifarnib and within 30 days of the last dose of tipifarnib.

Incidence rates and percentages will be summarized for each SOC and preferred term. A subject reporting multiple cases of the same TEAE will be counted once, at worst grade, within each system organ class and similarly counted once within each preferred term. All adverse events will be included in the listings. TEAEs will be tabulated in summary tables including:

- Overview of TEAE
- TEAEs by system organ class and preferred term
- TEAEs by preferred term, ordered by incidence
- TEAEs by system organ class, preferred term, and maximum CTCAE grade
- Treatment-related TEAEs by system organ class and preferred term
- Serious TEAEs by system organ class and preferred term
- Treatment-related serious TEAEs by system organ class and preferred term
- Treatment-related TEAEs by preferred term, ordered by incidence
- Serious TEAEs by preferred term, ordered by incidence
- Treatment-related TEAEs by system organ class, preferred term, and maximum CTCAE grade

Listings will be presented as follows:

- All AEs
- Serious AEs

- Treatment-related serious AEs
- AEs leading to discontinuation of tipifarnib
- AEs leading to death

Imputation rule for the missing AE onset date

AE onset date will be imputed only if day is missing, and only for the purposes of determining whether or not an AE is treatment emergent. All efforts will be made to query the sites to provide the missing information. For the partial date with missing day, the following imputation rule will be applied:

- If only day is missing, and if the year and month are equal to the first dose date, the day will be imputed as day of the first dose date. Otherwise, the day will be imputed as "01".

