## **10.7 Events Not to Be Considered as AEs/SAEs**

Medical conditions that are present at the initial study visit that do not worsen in severity or frequency during the study are defined as Baseline Medical Conditions and are NOT to be considered AEs. Progression of underlying disease is not an AE and therefore not an SAE per se, rather an efficacy end-point, unless deemed to be causally related to administration of IPs. However, if adverse signs or symptoms occur in association with disease progression then these should be recorded as AEs and reported as SAEs if meeting any seriousness criteria.

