## **10.9 Adverse Event Reporting Period**

The AE reporting period for safety surveillance begins when the subject is included into the study (date of first signature of informed consent) and continues through the study's post-treatment follow-up period, defined as 30 days from the final administration of the study treatment or immediately before initiation of any other anticancer therapy, whichever comes first.

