9.2 Prior and concomitant medications

Prior and concomitant medications will be coded using the WHO Drug dictionary June 2016. Medications initiated prior to start of treatment and maintained during the study or initiated after start of treatment will be considered as concomitant medications. Medications administrated prior to and not continuing the study treatment will be considered as prior medications. Medications with partial or missing start date will be assumed to be concomitant medications, unless there is clear evidence (through comparison of partial dates or end date with the date of tipifarnib treatment) to suggest that the medications are not taken during study. Prior and concomitant medications will be summarized separately by anatomical therapeutic class (ATC) and preferred name. The by-subject listing for all prior/concomitant medications will be provided.

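### SAP 11.1 defines a TEAE by onset date alone, so an AE that starts before first dose and worsens on tipifarnib is left out of all ten listed AE summary tables if it keeps its original onset date

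*SAP*

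**What the plan says.** SAP 11.1 takes as treatment-emergent those "AEs with an onset on or after start of tipifarnib and within 30 days of the last dose of tipifarnib". The test uses dates only and does not mention a change in grade or seriousness of an event already under way. The same section then states "TEAEs will be tabulated in summary tables including" and lists ten tables, each of them a TEAE table. It also states "All adverse events will be included in the listings" and names five listings, none limited to TEAEs.

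Protocol 10.9 sets when events start to count: "The AE reporting period for safety surveillance begins when the subject is included into the study", which it ties to the date of consent. Protocol 8.1 allows screening to run up to 28 days before Cycle 1 Day 1.

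Protocol 10.7 keeps one group out of the AE data: "Medical conditions that are present at the initial study visit that do not worsen in severity or frequency during the study". A condition that does worsen is not exempt.

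On incomplete dates, SAP 11.1 says "AE onset date will be imputed only if day is missing" and, of the sites, "All efforts will be made to query the sites to provide the missing information". For medications, SAP 9.2 sets a default: "Medications with partial or missing start date will be assumed to be concomitant medications", unless other dates show that they were not taken during the study.

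**The concern.** The protocol treats worsening as reportable, but the SAP definition does not carry that through to the tables. A subject may develop fatigue between consent and first dose at a low grade and reach a high grade on drug. If the site updates the existing record, the onset date stays before first dose and the event is not a TEAE.

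The trial population makes such courses plausible. Inclusion criterion 6 (Protocol 7.1) admits some residual Grade 2 toxicities and toxicities judged irreversible. The eligibility criteria set no minimum neutrophil or platelet count, and the titles of protocol Tables 2 and 3 distinguish subjects with lower counts at baseline. Medical history at screening (Protocol 11.1) includes ongoing AEs.

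TEAEs are a named secondary endpoint (Protocol 6.2, SAP 5.1.2). The study is open label with no comparator (Protocol 9.7), so absolute incidence is the AE result, and no second arm would share and cancel the omission.

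**Working it through.** The plan gives no figure to reproduce, so the check compares the rules and then asks what a size estimate would need.

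**1. Which outputs depend on TEAE status.** Counting in SAP 11.1:

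| Output | Number listed | Restricted to TEAEs |
|---|---|---|
| AE summary tables | 10 | 10 |
| AE listings | 5 | 0 |

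The laboratory grade summaries and shift tables in SAP 11.2 are separate safety outputs and do not use the TEAE flag. They set baseline grade against worst post-baseline grade.

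**2. How each course of events is classified.**

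| Course | Onset date on record | TEAE under SAP 11.1? |
|---|---|---|
| New event on drug | On or after first dose | Yes |
| Event starts after consent and before first dose, worsens on drug, one record kept | Before first dose | No |
| Same course, worsening entered as a new AE | On or after first dose | Yes |
| Baseline condition worsens on drug | Not stated: start of the condition or date of worsening | Depends on the date used |
| Onset month or year unknown after queries | None to test | Not stated |

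Rows two and three are the same clinical course. They differ only in how the site records it.

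**3. Whether the documents settle the recording.** Protocol 10.8 has unfavourable changes recorded as AEs and asks each report for onset and resolution dates and severity. It does not say that the worsening of an AE already open starts a new record. It refers to the sponsor's CRF conventions, which are not part of these documents. The convention is therefore open on what can be read here.

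**4. Missing dates.** When only the day is missing and the month is that of first dose, the SAP sets the day to that of first dose, which makes the event treatment-emergent. That choice is cautious. For a missing month or year, nothing follows the site query: the event is neither counted nor excluded by any stated rule. SAP 9.2 fills the same gap for medications.

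**5. Size.** For a given preferred term, the undercount in percentage points would be

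undercount = 100 × *a* × *b* × *c*

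where *a* is the proportion of subjects with an AE of that term that began before first dose and is still open, *b* the proportion of those in whom it worsens on drug, and *c* the proportion of those kept as one record with no other qualifying onset of that term. The documents give none of the three, so no value follows. The direction does: the omission can remove a subject from a numerator but cannot add one.

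**The case against.** The strongest reply is that the protocol already deals with most pre-existing problems. Conditions present at the first visit are baseline conditions and not AEs (Protocol 10.7). They become AEs only on worsening, and Protocol 10.8 has unfavourable changes recorded. On a natural reading the AE then starts at the worsening, after first dose, and meets the SAP definition. This stands as a plausible reading and narrows the clear-cut problem to AEs that first arise between consent and first dose and stay on one record. It does not close the gap, because no section states the onset date to use and the result is left to site practice.

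The second reply is that other outputs show worsening. Shift tables capture a deepening cytopenia directly. With the AML cohorts held and the report limited to CMML and MDS/MPN (SAP 4), the planned number is about 20 + 36 = 56 subjects, so listings can be read through. This also stands in part. A reader might infer that worsened events vanish from every safety table, and the documents do not support that. However, shift tables cannot show worsening fatigue or confusion, the dose-limiting toxicities in the phase 1 study described in Protocol 5.1.3. Nor do they show relatedness or seriousness, and listings give no incidence.

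Third, safety is descriptive and no stated decision rule uses the TEAE flag. That is correct and limits the weight of the point, but it does not make the incidence tables right.

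**Conclusion.** The definition in SAP 11.1 omits worsening, and every AE summary table listed there inherits the omission. The loss is conditional: it affects an AE with onset before first dose that worsens in grade or becomes serious on tipifarnib and keeps its original onset date. Where this happens, TEAE incidence is biased downward.

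Two stronger readings should be avoided:

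- A reader might put a percentage on the undercount. The neutropenia (18%) and thrombocytopenia (32%) rates quoted in Protocol 5.1.3 are event rates from an earlier study and say nothing about how many events would be missed here.
- A reader might conclude that AEs with an unknown onset month or year are excluded. The SAP leaves them unclassified after site queries. On its own that would be missing detail rather than a fault in the analysis.

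The conclusion rests on the protocol and SAP text alone. If the CRF conventions require a new record for every worsening, the practical effect would be small and the change would mainly put that rule on paper. The point bears on a secondary safety endpoint and does not touch the ORR analyses.

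**What to change.** In SAP 11.1, define a TEAE as either of the following, up to 30 days after last dose:

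- an AE with onset on or after first dose; or
- an AE or baseline condition present before first dose that increases in CTCAE grade or becomes serious on or after first dose.

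As a secondary clarification, add that an AE whose onset month or year is still missing after site queries counts as treatment-emergent unless the partial date or the end date shows otherwise, parallel to SAP 9.2.

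The cost is two SAP sentences and a change to one derived flag, best made before the tables are produced. To apply the worsening clause, the data must show when a grade changed or an event became serious, so it is worth confirming that the CRF captures this for an event kept on one record. The downside is that TEAE rates may come out slightly less favourable.

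### The rule for a missing AE onset day ignores the AE end date, so an event that ended before the first dose in the first-dose month is classed as treatment-emergent

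*SAP*

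**What the plan says.** SAP 11.1 defines TEAEs as "defined as AEs with an onset on or after start of tipifarnib and within 30 days of the last dose of tipifarnib". The definition uses onset and no other date.

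Where only the onset day is missing, the same section imputes it. In the month and year of the first dose, "if the year and month are equal to the first dose date, the day will be imputed as day of the first dose date". In any other month the day becomes the first of that month. The section limits the use of the imputed date: it serves "only for the purposes of determining whether or not an AE is treatment emergent". It also commits to data cleaning first: "All efforts will be made to query the sites to provide the missing information". The AE end date is not mentioned.

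Protocol 10.9 says that AE reporting "begins when the subject is included into the study (date of first signature of informed consent"), and SAP 6.1.1 places screening at Day -28 to Day -1. Protocol 10.8 requires onset and resolution dates in each AE report.

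For medications with a partial or missing start date, SAP 9.2 assumes concomitant use unless there is clear evidence against it, obtained "through comparison of partial dates or end date with the date of tipifarnib treatment".

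**The concern.** Assigning the first-dose date is a usual cautious choice when the timing of an event relative to dosing is unknown. The rule applies it even where the timing is known. An AE that began and resolved during screening, within the calendar month of the first dose, is moved to a date after its own end and becomes treatment-emergent. The database holds the date that shows otherwise, and the plan uses that kind of evidence for medications but not for AEs.

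The AE profile is a secondary objective, and every AE summary table in SAP 11.1 is restricted to TEAEs. In an uncontrolled study with small columns, a single misplaced event is visible in the incidence of its preferred term.

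**Working it through.** The plan gives no figure to reproduce here. The check applies the rule literally to test records and then sets out the size of one misclassified event.

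**Can such records exist, and be recognised?** Yes. AEs are recorded from consent (Protocol 10.9), over a screening period of up to 28 days (SAP 6.1.1), and are assessed again before the first dose on Cycle 1 Day 1 (Protocol 11.2). Resolution dates are collected (Protocol 10.8).

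**Literal application.** Assumed first dose: 20 June. The dates are illustrative.

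| True onset | Recorded onset | End date | Imputed onset | TEAE under SAP 11.1 | TEAE with an end-date check |
|---|---|---|---|---|---|
| 5 June | June, day missing | 12 June | 20 June | Yes | No |
| 28 May | May, day missing | 12 June | 1 May | No | No |
| 15 June | June, day missing | 25 June | 20 June | Yes | Yes |
| 22 June | June, day missing | 30 June | 20 June | Yes | Yes |

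Only the first record is wrong: its imputed onset falls 20 - 12 = 8 days after its end. The end-date check changes that record and no other.

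**Which tables are affected?** SAP 11.1 lists ten TEAE tables:
- four are general (overview; by class and term; by term; by class, term and maximum grade);
- four are restricted to treatment-related TEAEs;
- two are restricted to serious TEAEs.

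Relatedness and seriousness come from the investigator, not from the imputation. A non-serious, unrelated event reaches the four general tables only.

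**Size of one event.** SAP 11 reports safety on the Full Analysis Set in columns for CMML, MDS/MPN and Total. Planned sizes are about 20 CMML subjects and about 36 MDS/MPN subjects (SAP 5.2; Protocol synopsis). One added subject with a given preferred term contributes:
- CMML: 1/20 = 5.0 points
- MDS/MPN, both cohorts full: 1/36 = 2.8 points
- Total: 1/(20 + 36) = 1/56 = 1.8 points

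Actual column sizes may differ. If both MDS/MPN cohorts stopped after stage 1, that column would hold 7 + 7 = 14 subjects and one event would add 1/14 = 7.1 points. Subjects who are dosed and then replaced would enlarge the denominators. A subject who also has a genuine TEAE of the same term adds nothing, because each subject counts once per term.

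**How often could the calendar condition be met?** Assume a 30-day month, a first-dose day d uniform on 1 to 30, and a pre-dose onset uniform over the 28 preceding days. The share of pre-dose onsets in the first-dose month is the mean of min(d - 1, 28)/28, which is (406 + 28)/(28 x 30) = 0.517. So the calendar condition alone is not rare. It is only one of the conditions needed: the onset day must also be missing after queries, and the end date must precede the first dose. The documents give no probability for either.

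**The case against.** The strongest defence is that the rule is conservative and its reach is narrow. It can only over-report TEAEs. There is no comparator and no hypothesis test on AEs, no efficacy decision uses TEAE status, and all AEs are listed. An affected event must start after consent, since a condition present at the first visit that does not worsen is not an AE (Protocol 10.7). It must resolve before dosing, fall in the first-dose month, have a known end date but an unknown onset day, and survive the site queries. All of this stands, and it keeps the point minor. It does not justify the rule: caution is for unknown timing, and here the timing is known.

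Four stronger readings are tempting, and the documents do not support them.

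- *Negative AE durations result.* The imputed date may be used only to decide treatment emergence, and the SAP plans no AE-duration analysis. The onset falls after the end date only inside that classification step.
- *The event enters every TEAE table.* Six of the ten tables carry a further criterion. An event that ended before dosing is unlikely to be rated related, because temporal relationship is among the causality factors in Protocol 10.3.
- *One event adds 1/18 = 5.6 or 1/16 = 6.3 points.* Eighteen is the size of a single CXCR4/2 cohort and 16 is the number of evaluable initial CMML subjects (9 + 7). Neither is a planned safety column.
- *About half of pre-dose AEs with a missing onset day are misclassified.* The 52% includes events still ongoing at dosing, or with unknown end dates, which properly stay treatment-emergent.

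**Conclusion.** The point holds as a minor defect. As written, SAP 11.1 classes as treatment-emergent an AE that its own end date shows was over before the first dose, when the onset day is missing and the onset month is that of the first dose. No other section of either document supplies an end-date exception for AEs.

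The direction is over-reporting. The number of affected events cannot be derived, because it depends on how many onset days remain missing after queries. Per event, the effect is about 5.0 points in the CMML column and 2.8 points in the MDS/MPN column. These figures assume that the Full Analysis Set columns reach their planned sizes and that the subject has no other TEAE of the same term. The correction is desirable; no conclusion of the trial turns on it.

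**What to change.** Add to the imputation rule in SAP 11.1: *unless a complete or partial AE end date shows that the event ended before the first dose date, in which case the AE is not treatment-emergent.* This matches the end-date comparison in SAP 9.2. In practice the exception will act mainly on complete end dates, since an end date known only to the first-dose month does not show that the event ended before dosing.

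Events with an unknown end date, or one on or after the first dose, stay treatment-emergent, so the cautious default is kept where timing is uncertain. The cost is one clause in the SAP and one condition in the program. No new data are needed, because resolution dates are already collected.

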11.2 Clinical laboratory evaluations

All clinical safety laboratory tests listed in the section below will be performed at local laboratories. Subject eligibility will be determined based on the baseline laboratory results. Clinically significant laboratory test abnormalities will be followed until resolution or stabilization and the overall clinical outcome has been ascertained (See protocol Section 10.4).

Blood samples will be collected for the following clinical laboratory tests:

- Serum Chemistry: aspartate aminotransferase (AST), alanine aminotransferase (ALT), total bilirubin, creatinine, potassium and calcium
- Hematology: hemoglobin, platelets, white blood cells (WBCs), neutrophils, neutrophil precursors, lymphocytes, monocytes and blasts
- Coagulation: activated partial thromboplastin time (APTT), prothrombin time/international normalized ratio (PT/INR)

All hematology, blood chemistry, coagulation results will be listed per subject for each assessment. Descriptive statistics will be tabulated by visit based on actual value and change from baseline value.

Laboratory values will be graded and summarized based on NCI CTCAE v4.03. Shift tables will be provided for applicable laboratory tests to summarize the frequencies of subjects by CTCAE grade at baseline contrasted with worst post-baseline values.

11.3 Bone marrow

Data of bone marrow aspirate and biopsy will be tabulated by visit. Descriptive statistics will be presented for tests with continuous results (i.e., Myeloblasts (%) and cellularity (%)). Counts and percentages of subjects will be provided for tests with categorical results. The by-subject listing will be provided.

11.4 Myeloproliferative neoplasm symptom assessment score

Data of MPN symptom assessments will be listed per subject for each assessment. Descriptive statistics will be tabulated for each symptom based on actual value and change from baseline value.

11.5 ECOG performance status

Data for ECOG performance status are collected on Screening, Day 1 of each cycle, and End of Treatment visit. Subject counts and percentage under each ECOG category will be

summarized by visit for both actual value and change from baseline value. The by-subject listing for all ECOG data will be provided.

11.6 Physical exam and vital signs

Complete physical examination, including vital signs, is performed on Screening and End of Treatment visit. Symptom-based physical exam is performed on Day 1, Day 15 and Day 25 of each cycle and as needed throughout the study. Data of vital signs (heart rate, blood pressure, and temperature) will be tabulated using descriptive statistics based on actual value and change from baseline value at each scheduled time point. The by-subject listings will be provided for all data of physical exam and vital signs.

Body weight will be listed per subject for each assessment. Descriptive statistics will be presented by visit based on actual value and change from baseline value.

11.7 Cytogenetics

Cytogenetics data will be listed by assessment and subject.

11.8 Other data related to safety

A by-subject listing will be provided for pregnancy tests and other data.

